## g. Statistical Methods

### i. Data Analysis Plan

The analytical plan does not change due to the increase in intervention period from 4 to 8 weeks.

Descriptive statistics and clustering (e.g., principal components analysis [PCA]), will be performed for all biomarker data measured at the different visits. Baseline data (1st bronchoscopy) will then be compared between the four groups (3 conditions and control) using a one-way analysis of variance (ANOVA). The non-parametric Kruskal-Wallis test (continuous or ordinal variables) or the chi-square test (categorical variables) will be applied when the normality assumption of the data is not met. We will compare controls to complete substitution with the SREC (with and without nicotine) or NRT conditions. Generalized linear models (GLM) will be employed with measurement (cell count, gene expression, etc.) as the dependent variable, a covariable for baseline measure, and a main effect of arm. Other relevant variables that are associated with the biomarker results, e.g., baseline smoking, FTND, or gender will also be included in our models as they are potential confounders. We also will assess batch effects and include batch as a co-variable in the model (all samples will be analyzed at the same time, except for cell counts). We plan to use baseline molecular measurement as a covariable rather than modeling the change between baseline and follow-up because the former is more powerful [300]. Given the large dynamic range of the cell count and the 'omics data, we will initially consider a normal distribution. If the data are determined to deviate from normality, we will log-transform the data or assume a non-normal distribution of residuals (such as Poisson) for the GLM. Urine PG will be measured at the 2nd bronchoscopy visit and compared to baseline to verify e-cig use. As an exploratory analysis, urinary PG will be used as the exposure predictor variable assessing the biomarker results as dependent variables. Urine anatabine, urine anabasine and nicotelline will be used to confirm complete substitution or a predictor variable for smoking reduction. The cotinine level will be used as a surrogate for smoking reduction.

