**The Effects of a Standardized Research E-Cigarette on the Human Lung:
A Clinical Trial with Bronchoscopic Biomarkers**

NCT03691350

Statistical Analysis Plan, 09/19/22

SREC SAP

The Specific Aim for this two year project is:

To assess inflammatory changes over 10 weeks (8 weeks experimental condition) for lung and urine biomarkers in smokers in a clinical trial where smokers are randomized to: continued use (n=32), complete switching to the nicotine standardized research electronic cigarette (SREC) (n=32), complete switching to the placebo SREC (n=32), or complete switching to nicotine replacement therapy (NRT) (n=32).

- 1) We will enroll 128 subjects (32 per group). For power calculations, we will use a conservatively planned 66% retention rate at 5 weeks, knowing that we have a 100% retention for never smokers receiving serial bronchoscopies. Thus, the final sample size will be 21 subjects per group (n=84). Although we expect a higher retention rate, we assume 66% to ensure that we have the minimal numbers required to reach meaningful conclusions. Since follow-up samples would not be obtained from subjects that do not finish the treatment protocol, and these samples (inflammation/omics) are our primary outcomes, we cannot use an 'intent to treat' strategy since dropouts will have missing outcome data for any analyses including follow-up measurements (the primary Aim). In light of this, we will compare dropout rates between arms and with demographic/clinical to ensure that the analyses results are not biased by unbalanced dropouts. We will also test for differences in baseline molecular measurements between subjects that dropout after baseline samples are taken vs. subjects that complete the protocol. While we will make every effort to minimize the missing data for this study, missing data can arise due to various reasons. Violation of missing completely at random (MCAR) will be checked by evaluating whether any covariates are associated with missing data. If so, these covariates will be subsequently included and controlled for in the GL(M)M models. In addition, sensitivity analyses will also be conducted using results from multiple imputation.

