The 'omics' (miRNA, mRNA and metabolomics) analysis and visualization of the data will be performed in the R statistical language. Data will be log2-transformed and normalized using either quantile normalization for gene expression (miRNA and mRNA) or TIC/MSTUS normalization for metabolomics. Unsupervised clustering analysis, including PCA and hierarchical clustering will be performed to visualize natural clusters in the dataset and evaluate data quality. Multiple testing corrections using the Benjamini and Hochberg False Discovery Rate (FDR) will be performed. Significantly altered genes and metabolites will be defined as those with FDR corrected p-value < 0.05 and fold changes > 2 or > 1.5, respectively. Identified genes or metabolites will be used to identify relevant networks and pathways using Ingenuity Pathways Analysis. For gene expression, we will further study associations between miRNA-mRNA pairs based on publically available target prediction databases such as TargetScanHuman, miRDB, miRWalk2.0 and others. Global integrative analysis, through correlations, will be performed using Partek software.

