Power is provided for a t-test [2]. Expression/metabolomics/proteomics data tend to follow Gaussian distributions, although there can be violations within each platform. With the large number of variables present in 'omics data, it is intractable to evaluate the appropriateness of the model for each individual variable. Therefore, we use the overall distribution across all variables within a platform to assume a distribution. While individual variables may randomly deviate from the model assumptions (normality, in most cases), if the overall distribution is Gaussian we assume that each of the features was sampled from the overall Gaussian. However, to check if assumptions are causing spurious positive results, we will test each associated feature, post hoc, for departures from the model assumptions. Cell counts were also considered Gaussian for these power calculations. While counts are inherently discrete, because the expected cell counts are very large ($>2E+07$), Gaussian should be a good approximation for this distribution. The parameters included in the power calculation are the CVs, the p-values, and the effect sizes. The CVs used were estimated from preliminary data (and similar data from other studies). The effect sizes assumed are reasonable (smaller) compared to the effect sizes we see in the preliminary data. The p-values used were stringent to adjust for multiple comparisons. Because, especially with 'omics data, we do not know a priori the number of tests, we use significance thresholds that correspond to an expected number of false discoveries per number of tests to control for multiple comparisons without defining the number of tests. For the primary analyses, we accept that one expected false discovery per 10,000 tests is a reasonable error rate. In practice, we will use FDR to determine the expected fraction of false discoveries for assuming a particular significance threshold. For a final sample size of 21 in the control group and 21 in each use condition, for a two-sided analysis, we have 80% power to detect ≥ 1.5 -fold difference in cell counts/cytokine levels between each condition and controls for a two-sample t-test. For gene expression/metabolomics data, with the same considerations except a CV=0.5 (approximate from many gene expression data sets with which we have worked), we have 80% power to detect ≥ 2.1 -fold differences.

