- 4) For mtDNA features, Model 1 is also used. CN is expected to be Gaussian, while mutation rate is expected to be low counts; therefore, a t-test was powered for CN and Poisson [3] for mutation rate. Because there will only be several comparisons here, the significance threshold used for power corresponds to one expected false discovery per 100 tests. We believe that this threshold is a good balance between potential Type I and Type II errors, given the number of tests. The coefficient of variation was calculated from results in the

literature, as cited in the main body of the protocol. For CN, with 21 samples per group, considering a significance threshold of 0.01, a two-sided, two-sample t-test achieves 80% power to detect an 1.4 fold difference between arms considering a coefficient of variation of 0.32 [4]. For mutation, Poisson regression achieves 80% power to detect a mutation rate ratio of 2.7 between arms considering a significance threshold of 0.01 and 21 samples per group [5].

- 5) For associations between mtDNA and other 'omics features, we assume the regression model [6]:

$$\text{Followup_Expression} = \text{Baseline_expression} + \text{arm} + \Delta\text{mtDNA feature} + e,$$

Where $\Delta\text{mtDNA} = \text{Followup_mtDNA} - \text{Baseline_mtDNA}$. We consider this model across all arms. The effect of arm is included as a covariable to ensure that associations are not simply due to both features being associated with arm; rather, we are looking for a more direct relationship. Again, we consider a significance threshold corresponding to one expected false discovery per 10,000 tests, as described above. To generalize, we assume unit standard deviations of the dependent and independent variables (each feature will have a different standard deviation, so results are calculated in terms of standard deviations). With 84 samples, considering a significance threshold of $p=0.0001$ and unit standard deviations for dependent variable residuals and ΔmtDNA features, linear regression achieves 80% power to detect a slope of 0.48.

- 6) For comparing mtDNA features between nasal and bronchial samples, mixed Poisson or mixed Gaussian will be employed with a random effect for subject, and a main effect for location (bronch vs. nasal):

$$\text{Feature} = \text{sample\&rand} + \text{location} + e.$$

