Poisson regression achieves at least 80% power to detect a mutation rate ratio of 2.1 between the sample origins considering a significance threshold of 0.01 and 84 paired samples. For mtDNA CN, a two-sided paired t-test achieves 80% power to detect a mean of paired differences of 0.4 standard deviations of the paired differences considering 84 paired samples and a significance threshold of 0.01. Correlations (CN) and Cohen's kappa (mutational burden) will also be calculated between the two tissues for each of the assays.

- 7) As a secondary aim, we will test if treatment is associated with differences in mtDNA genetic features between tissues. Generalized linear mixed models will be employed with measurement (mtDNA genetic features) as the dependent variable, a random effect for patient, covariables for baseline measure and sample origin, a main effect of arm, and an interaction effect of origin* arm:

$$\text{Feature} = \text{sample\&rand} + \text{baseline} + \text{origin} + \text{arm} + \text{arm*origin} + e.$$

This analysis will investigate whether treatment is associated with differences between tissues. The interaction term will be comprised of four groups of 21 for each pair of arms.

To conservatively estimate the power to detect this interaction effect, the power will be calculated while adjusting the significance threshold for the number of pairwise tests ($n=6$; $p=0.01/6=0.0017$). A two-sided, two-sample t-test achieves 80% power to detect an 1.5 fold difference between any two groups considering a significance threshold of 0.0017, 21 samples per group, and a coefficient of variation of 0.32 [4].

- 8) As an additional exploratory analysis, we will study dose-response associations of cigarette smoking with biomarkers at baseline bronchial and nasal samples separately. Generalized linear models (again, Poisson or Gaussian) will be fit with biomarkers as the dependent variable and covariables (e.g., cigarettes per day [cigs/day] and urinary cotinine levels, separately), adjusting for confounders, such as sex and age. THC use will also be examined.

References

1. Zhang, S., et al., *Empirical comparison of four baseline covariate adjustment methods in analysis of continuous outcomes in randomized controlled trials*. Clin Epidemiol, 2014. **6**: p. 227-35.
2. Julious, S.A., *Sample sizes for clinical trials with normal data*. Stat Med, 2004. **23**(12): p. 1921-86.

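### Several stated power figures do not match the plan's own gene decision rule, SD convention, interaction contrast or outcome time; the gene figure is the clearest case

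*SAP*

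**What the plan says.** **Gene rule.** Protocol 4.g.i and SAP item 2 define significantly altered genes and metabolites by "FDR corrected p-value < 0.05 and fold changes > 2 or > 1.5, respectively". Both conditions must be met, with 2 for genes and 1.5 for metabolites. Protocol 4.g.ii and SAP item 3 claim 80% power for differences of 2.1-fold or more from a two-sample t-test at alpha 0.0001 with 21 per group, "with the same considerations except a CV=0.5 (approximate from many gene expression data sets with which we have worked". The fold cut-off plays no part in that calculation.

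**Slope.** SAP item 5 says that at N = 84 and alpha 0.0001 "linear regression achieves 80% power to detect a slope of 0.48". The same paragraph gives two conventions: unit SDs for the dependent and independent variables, then unit SDs for the residuals of the dependent variable and for the mtDNA change. Protocol 4.g.ii gives only the residual version.

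**Interaction.** SAP item 7 and protocol 4.g.ii describe an arm-by-origin term built from four cells of 21 for each pair of arms. The SAP introduces the figure with "To conservatively estimate the power to detect this interaction effect", which refers to dividing alpha by six. The figure is 80% power for 1.5-fold between any two groups, with CV 0.32.

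**Retention.** SAP item 1 enrols 32 per arm and states "we will use a conservatively planned 66% retention rate at 5 weeks", giving 21 per arm. Protocol 4.e.iii places the follow-up specimens at about day 71. Protocol 4.g.i adds: "The analytical plan does not change due to the increase in intervention period from 4 to 8 weeks".

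**The concern.** A power statement tells a later reader what a null result rules out. It can do so only if it is computed for the rule, variance, contrast and sample size that will apply. Here the gene figure leaves out half of the decision rule. The slope figure depends on which of two incompatible sentences is meant. The interaction figure belongs to a different contrast. The sample size behind every figure uses a retention rate dated about five weeks before the outcome is measured. If these stand, a gene list without a given 2-fold change, or a null interaction, could be read as stronger evidence of no effect than the design provides.

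**Working it through.** **Common method.** Fold changes are taken on the log scale, SD = sqrt(ln(1 + CV²)), SE = SD × sqrt(2/n), with two-sided noncentral t on 2n − 2 df. Inputs are from SAP items 1 to 7 and protocol 4.g.ii unless marked as assumed.

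**1. Gene rule** (CV 0.5, n = 21, alpha 0.0001)
- SD = sqrt(ln 1.25) = 0.472; SE = 0.472 × sqrt(2/21) = 0.146.
- Plan's figure: at 2.1-fold, noncentrality = ln 2.1 / 0.146 = 5.09 and t-test power is 76%. Power reaches 80% at 2.143-fold, so the stated figure reproduces after rounding the fold change.
- Fold filter: P(observed fold > 2 given true 2.1) = Φ((ln 2.1 − ln 2)/0.146) = Φ(0.335) = 63%.
- Both conditions together:

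| True fold | t-test alone | t-test and observed fold > 2 |
|---|---|---|
| 2.10 | 76% | 61% |
| 2.143 | 80% | 66% |
| 2.28 | 89% | 80% |
| 2.30 | 90% | 82% |

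- A looser p cut-off does not help: at alpha 0.001 the t-test has 93% power at 2.1-fold, but joint power is 63%, the ceiling set by the filter.
- Metabolites: with the 1.5 cut-off, joint power at 2.1-fold stays at 76%.

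**2. Slope** (N = 84, alpha 0.0001, SD of predictor 1, df 82)
- Unit SD of the dependent variable: residual SD = sqrt(1 − 0.48²) = 0.877; noncentrality = 0.48 × sqrt(84)/0.877 = 5.01; power 81%. The slope for 80% is 0.476, so the plan's 0.48 reproduces.
- Unit SD of the residuals: noncentrality = 0.48 × sqrt(84) = 4.40; power 62%. The slope for 80% is 0.54.

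**3. Interaction** (CV 0.32, n = 21, alpha 0.01/6)
- Plan's figure: the two-group t-test at 1.5-fold gives 79%, so it reproduces.
- The interaction compares within-subject tissue differences between arms. With tissue correlation ρ, its SE is the two-group SE × sqrt(2(1 − ρ)). No ρ is given, so the values below are assumed.

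| ρ | Power at 1.5-fold |
|---|---|
| 0 | 36% |
| 0.3 | 58% |
| 0.5 | 79% |
| 0.7 | 97% |

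- The two calculations coincide at ρ = 0.5, where the multiplier is 1. At ρ = 0 the detectable fold is 1.78.

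**4. Retention**
- Plan's figure: 32 × 0.66 = 21.12, so 21. It reproduces.
- If dropout continued at the same rate to week 10 (assumed): 0.66² = 0.436, and 32 × 0.436 = 13.9, so 14.
- Sensitivity of the unadjusted t-test at alpha 0.0001:

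| Per arm | Cell counts, CV 0.26, 1.5-fold | Genes, CV 0.5, 2.1-fold, t-test alone |
|---|---|---|
| 21 | 78% | 76% |
| 18 | 63% | 62% |
| 16 | 51% | 50% |
| 14 | 39% | 37% |

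**The case against.** The plan's arithmetic largely reproduces, and SAP item 3 says openly that power is given for a t-test. The planned model also adjusts for baseline, which the power calculation ignores. With an assumed baseline correlation r of 0.3, 0.5 or 0.7, cell-count power at 1.5-fold and 21 per arm rises to 84%, 93% and over 99%; at 14 per arm it is 45%, 60% and 87%. That stands, and it rules out saying that every stated figure is too favourable. It does not rescue the gene figure: at 2.1-fold, joint power under the same three values of r is 63%, 65% and 68%, because the filter acts on the observed fold change.

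Three stronger readings are tempting and are not supported.
- **That only 14 per arm will be evaluable.** The SAP calls 66% conservative and expects better, neither document gives a day-71 rate, and 14 needs a constant-hazard assumption. The revision history records that sample size and power were updated when the intervention was lengthened, and again in 2022 to reflect attrition. The sentence about an unchanged analytical plan is not about retention. If 66% is in fact meant for day 71, 21 stands.
- **That slope 0.48 simply has 62% power.** One of the SAP's two conventions gives the stated result.
- **That the interaction figure is anti-conservative.** It is too favourable only for ρ below about 0.5. Both samples come from the same person, and the protocol's background treats nasal cells as a surrogate for the lower airway, so ρ = 0 is a worst case. Baseline adjustment would help too: ρ = 0.3 with r = 0.5 (both assumed) gives 76%. The analysis is also a secondary aim.

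**Conclusion.** The point holds as a mismatch between stated power and planned analysis, and it should be fixed. Confidence is moderate overall, because the four parts differ in strength.

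The gene part needs nothing beyond the plan's own inputs and the log-scale t-test: the rule in force has about 61% power at 2.1-fold, against 76% for the t-test alone, and 80% is reached near 2.28-fold. A reader might say that the filter cuts power from 80% to 61%. That mixes two fold changes: the fall is from 76% to 61% at 2.1, or from 80% to 66% at 2.143.

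The slope part is a contradiction in SD wording within the SAP, and a protocol sentence that does not match its own figure. The interaction part is a power figure for the wrong contrast, with its conservatism not shown. The retention part is a missing assumption at the outcome time, not a demonstrated shortfall.

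**What to change.** - **Genes:** in SAP item 3 and protocol 4.g.ii, state power under the full rule, with about 2.3-fold for 80% (unadjusted). Leave the metabolite statement, noting that its cut-off does not bind.
- **Slope:** use one convention in both documents: unit SD of the dependent variable with 0.48, or unit residual SD with 0.54.
- **Interaction:** power the 2 × 2 contrast over a stated range of tissue correlations, such as 0 to 0.7, and do not call the figure conservative unless a correlation is given and justified.
- **Retention:** state the assumed day-71 retention and its basis, and show power at 21, 18, 16 and 14 per arm, with 14 labelled as a constant-hazard assumption. If credit is taken for baseline adjustment, state the assumed correlation.

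The cost is recalculation and matching edits to the two documents. No design change or new data are needed. The gene figure becomes less favourable; the others may or may not, depending on the assumptions chosen.

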  - (1) Total and inflammatory cells: Total cell counts will be measured by 1:1 dilution in trypan blue and instillation into disposable Countess™ cell counting chamber slides [292]. Automated cell counts and viability will be evaluated by the Countess® Automated Cell Counter according to the manufacturer's instruction (Invitrogen, Carlsbad, CA). Differential counting will be performed on Diff-Quik stained cytopspins [293] and at least 200 cells will be counted on each preparation according to standard morphologic criteria under light microscopy. Differential cell counts will be evaluated by a histopathologist at OSUCCC.

- (2) Cellular component: Part of cells recovered from the BAL and nasal fluid will be lysed to measure expression of innate immune regulatory molecules. The remaining cells will be cultured up to 24h to determine their responsiveness to exogenous stimuli by quantitating newly released and newly produced intracellular molecules.
- (3) Cytokines: Inflammatory cytokines, TNF alpha and total protein concentration in the lavage fluid will be assessed using laboratory techniques including but not limited to MSD and ELISA assays, and cellular expression of these will be assessed on the cellular components by immunohistochemistry as previously described [294].
- (4) Glycerol and propylene glycol: Mass spectrometry methods. The assays will be developed and performed in the Nutrient Phytochemical Shared Resource of the OSUCCC, as previously described [182, 183, 290].
- (5) Untargeted metabolomics: mass spectrometry methods. These assays will be done in the Nutrient Phytochemical Shared Resource of the OSUCCC.
- (6) Cytometry by Time of Flight (CyTOF) analysis: Using a mass spectrometry technique based on inductively coupled plasma spectrometry and time of flight mass spectrometry will determine the cellular expression, properties of cells (cytometry) to distinguish inflammatory cell subtypes.
- (7) Tobacco use biomarkers: will be analyzed for validation of smoking cessation, the measurement of extent of tobacco use, and assessing exposure. This will include cotinine (metabolite of nicotine), nicotine, 3-hydroxycotinine, polycyclic aromatic hydrocarbons, NNAL (metabolite of tobacco-specific nitrosamines), anatabine and anasabine (tobacco alkaloids), mercapturic acids (metabolites of volatile organic compounds, and untargeted metabolomics.

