## **ii. Sample Size and Power**

We will enroll 128 subjects (32 per group). For power calculations, we will use a planned 66% retention rate at 5 weeks, based on the clinical trial discussed above, and knowing that we have a 100% retention for never smokers receiving serial bronchoscopies. Thus, the final sample size will be 21 subjects per group ( $n=84$ ) For the purposes of sample size considerations, we will consider cell counts based on the current available data in the cross-sectional study comparing smokers to e-cig users, as indicated above. Based on our current data of smokers undergoing bronchoscopy, the mean cell count for the smokers was  $2.41E+07$  ( $1.48E+07$ ) and the e-cig users was  $4.03E+07$  ( $4.84E+07$ ). In the preliminary cross-sectional study, we see decreases in cell counts of

~2.5 fold with e-cig use. For our power calculations we will assume a CV = 0.26 (from the healthy smokers undergoing bronchoscopy). For power, because of the large number of tests (the total number is currently unknown because of unknown numbers of metabolites and gene expression passing filtering), we will assume a significance threshold that corresponds to one expected false discovery per 10,000 tests (0.0001). Thus, for a final sample size of 21 in the control group and 21 in each use condition, for a two sided analysis, we have 80% power to detect  $\geq 1.5$ -fold difference in cell counts/cytokine levels between each condition and controls for a two-sample t-test. For gene expression/metabolomics/proteomics data, with the same considerations except a CV=0.5 (approximate from many gene expression data sets with which we have worked), we have 80% power to detect  $\geq 2.1$ -fold differences.

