- 2) Descriptive statistics and clustering (e.g., principal components analysis [PCA]), will be performed for all biomarker data measured at the different visits. Baseline data (1st bronchoscopy) will then be compared between the four groups (3 conditions and control) using a one-way analysis of variance (ANOVA). The non-parametric Kruskal-Wallis test (continuous or ordinal variables) or the chi-square test (categorical variables) will be applied when the normality assumption of the data is not met. We will compare controls to complete substitution with the SREC (with and without nicotine) or NRT. Generalized linear models (GLM) will be employed with measurement (cell count, gene expression, etc.) as the dependent variable, a covariable for baseline measure, and a main effect of arm. Other relevant variables that are associated with the biomarker results, e.g., baseline smoking, Fagerstrom Test for Nicotine Dependence (FTND), or gender will also be included in our models as they are potential confounders. We also will assess batch effects and include batch as a co-variable in the model (all samples will be analyzed at the same time, except for cell counts). We plan to use baseline molecular measurement as a covariable rather than

modeling the change between baseline and follow-up because the former is more powerful [1]. Given the large dynamic range of the cell count and the 'omics data, we will initially consider a normal distribution. If the data are determined to deviate from normality, we will log-transform the data or assume a non-normal distribution of residuals (such as Poisson) for the GLM. Urine propylene glycol (PG) will be measured at the 2nd bronchoscopy visit and compared to baseline to verify e-cig use. As an exploratory analysis, urinary PG will be used as the exposure predictor variable assessing the biomarker results as dependent variables. Urine anatabine, urine anabasine and nicotelline will be used to confirm complete substitution or a predictor variable for smoking reduction. The cotinine level will be used as a surrogate for smoking reduction.

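### The fallback for non-normal BAL cell counts allows a plain Poisson model, which is invalid for totals near 2.4E+07: if used in single-cell units with dispersion fixed at 1, it would reject about 99.9% of true nulls at 0.05

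*SAP*

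**What the plan says.** SAP item 2 fits a generalized linear model with "measurement (cell count, gene expression, etc.) as the dependent variable, a covariable for baseline measure, and a main effect of arm". On the distribution it says "Given the large dynamic range of the cell count and the 'omics data, we will initially consider a normal distribution", and then: "If the data are determined to deviate from normality, we will log-transform the data or assume a non-normal distribution of residuals (such as Poisson". Protocol section 4.g.i carries the same rule, ending "assume a non-normal distribution of residuals (such as Poisson) for the GLM".

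Neither document gives a rule for choosing between the two routes, a test for normality, or a unit for the cell total. Neither mentions an estimated dispersion, a negative binomial model or a robust variance.

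SAP item 1 makes the inflammation and 'omics measurements the primary outcomes, and Protocol section 4.g.ii bases the sample size on cell counts.

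**The concern.** A Poisson model takes its standard error from the size of the numbers, because it sets the variance equal to the mean. That can suit a small tally of independent events. It does not suit a total of tens of millions that varies several-fold between people. The standard error is then far too small and almost any two arms differ significantly. The result also changes with the unit in which the total is recorded.

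The laboratory method points the same way. Protocol section 4.d.iii says "Total cell counts will be measured by 1:1 dilution in trypan blue", read in a chamber slide, and the bronchoscopy procedure recovers about 40-60 ml of fluid. A total near 2E+07 is therefore presumably a small reading scaled up. The documents do not write out that step, and the figures below do not depend on it.

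At stake is the validity of the test for the outcome used to size the trial, should this route be taken.

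**Working it through.** **Inputs**
- Mean: Protocol section 4.g.ii, "the mean cell count for the smokers was" 2.41E+07, followed in brackets by 1.48E+07, read here as an SD. CV = 1.48/2.41 = 0.614.
- Planning value, same section: "we will assume a CV = 0.26 (from the healthy smokers undergoing bronchoscopy". This is the case kinder to Poisson.
- Group size: 21 v 21 (SAP items 1 and 3), two-sided.

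**The plan's own figure.** The documents state no type I error for the Poisson route. The related figure is the 1.5-fold detectable difference at 80% power and alpha 0.0001. On the log scale the SD is √ln(1 + 0.26²) = 0.2558. With 21 v 21 (noncentral t, 40 df) the standardised difference detectable at 80% power is 1.613, and exp(1.613 × 0.2558) = 1.51. The stated 1.5 is reproduced, and the same method gives 2.14, 1.41 and 1.505 for the stated 2.1, 1.4 and 1.5 elsewhere. The documents do not say the log scale was used, but it fits their fold differences.

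**Poisson against the data.** A Poisson variable with mean 2.41E+07 has SD √2.41E+07 ≈ 4,909. The pilot SD is 1.48E+07/4,909 ≈ 3,015 times larger. With CV 0.26 the SD is 0.26 × 2.41E+07 = 6.27E+06, about 1,276 times larger.

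**Type I error, no baseline covariate.** For group sums A and B the Poisson statistic is z = (ln A − ln B)/√(1/A + 1/B). If the true variance is φ times the mean, z has variance about φ under the null, so

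P(reject) = 2 × [1 − Φ(1.96/√φ)], with φ = CV² × mean in the reporting unit.

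In single cells, φ = 0.26² × 2.41E+07 = 1.63E+06, or 0.614² × 2.41E+07 = 9.09E+06. Recording the total in numbers 1,000 times larger multiplies φ by 1,000 and z by √1,000 ≈ 32.

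| Unit of the total | φ, CV 0.26 | Null rejected at 0.05 | φ, CV 0.614 | Null rejected at 0.05 |
|---|---|---|---|---|
| single cells | 1.63E+06 | 99.88% | 9.09E+06 | 99.95% |
| thousands | 1,629 | 96.1% | 9,086 | 98.4% |
| hundreds of thousands | 16.3 | 62.7% | 90.9 | 83.7% |
| millions | 1.63 | 12.5% | 9.09 | 51.6% |
| tens of millions | 0.163 | about 0% | 0.909 | 4.0% |

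At the stringent 0.0001 threshold, single cells still give 99.76% and 99.90%.

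**With the planned baseline covariate.** Simulation: 1,500 null trials per setting, lognormal values, log baseline as covariate, baseline to follow-up correlation assumed at 0, 0.5 and 0.8. In single cells the null is rejected in 99.7% to 100% of trials. Adjustment matters only in coarse units: in millions with CV 0.614, rejection is 49.7%, 46.3% and 30.9% across the three correlations.

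**Alternatives on the same basis** (correlation 0.5; CV 0.26 then 0.614):
- log-transform with a linear model: 4.3%, 5.8%
- Poisson mean with estimated dispersion: 3.9%, 6.1%
- Poisson with robust (HC1) errors: 6.7%, 7.5%

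The simulation standard error near 5% is √(0.05 × 0.95/1,500) ≈ 0.6 points. Robust errors run slightly high; all three are near nominal.

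**The case against.** The strongest reply is that Poisson appears only as a bracketed example inside the second of two options, with log-transformation named first. SAP item 3 treats cell counts as approximately Gaussian because they are so large. SAP item 4 uses Poisson for mtDNA mutations precisely because those counts are low, which suggests where the authors meant it to apply. Item 3 also promises a post hoc check of model assumptions for associated features, and a variance-to-mean ratio in the millions should fail any such check.

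Much of this stands, and it limits the point. A reader might infer that the plan as written will give 99.9% false positives. The documents do not support that: normality must be judged to fail, Poisson chosen over log-transformation, totals entered as single cells, and dispersion fixed at 1.

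A reader might also infer that Poisson is likely to be used. Non-normality is plausible: a normal curve with the pilot smoker figures puts about 5% of values below zero. But it depends on the CV. With lognormal data and a Shapiro-Wilk test at 0.05 (an assumption, since the plan names no test), it is flagged in 37% of 21 v 21 datasets at CV 0.26 and 90% at 0.61. Nothing says how often Poisson would then be picked.

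Nor are all platforms exposed. SAP item 2 and Protocol section 4.g.i already put miRNA, mRNA and metabolomics on the log2 scale and methylation on M-values. Cytokines are not named in the distribution sentence and come in only if given the same model.

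What the reply does not do is close the route. Item 3's Gaussian remark concerns power and does not withdraw the fallback. Its post hoc check is written mainly for 'omics features and names neither a dispersion check nor a consequence. The fold-change filter covers genes and metabolites, not cell counts.

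**Conclusion.** The concern holds in a conditional form. For total BAL cell counts, one of the two permitted fallbacks is an invalid test whose p-value depends on the reporting unit, and the plan has no rule that excludes it. If taken in single cells (the scale of the pilot figures) with dispersion fixed at 1, it rejects about 99.9% of true nulls at 0.05, with or without baseline adjustment. In millions of cells the rate without adjustment is about 12% to 52%, and in tens of millions about 0% to 4%.

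This rests on reading 1.48E+07 as an SD, or alternatively on the planning CV of 0.26; the single-cell result is the same under either. The mismatch between those two CVs is a separate matter. The simulations also assume a lognormal shape and the stated baseline correlations. Poisson for low-count mtDNA mutations (Protocol section 4.g.ii, SAP item 4) is not in question.

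**What to change.** In SAP item 2 and Protocol section 4.g.i, remove plain Poisson as an option for cell counts and cytokines, and pre-specify the model. For example:

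> BAL cell counts and cytokine levels will be analysed on the log scale with a Gaussian linear model containing log baseline and arm, and reported as geometric mean ratios with confidence intervals. If a count-type generalized linear model is used instead, dispersion will be estimated (quasi-Poisson, negative binomial or gamma) or a robust variance used.

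Geometric mean ratios match the fold-difference power statement. The choice among the listed fallbacks is open; what matters is that the variance is not fixed by the unit. The text should also say how zeros are handled for rare cell subtypes, since differentials are read on as few as 200 cells and a zero has no logarithm.

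The cost is a short wording change in each document. It needs no new data and no change in sample size, and log-transformation is already the first-named option.
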